5.2 Handling of Study Interventions

Due to the nature of the intervention, participants, pharmacists and PCPs cannot be masked. Project assistants will enter data into a REDCap database so that the researchers can analyze it without having access to group assignment.

We will use multiple strategies to implement and measure fidelity in the study:

Training Fidelity: Training materials for pharmacists will consist of guiding questions to help elicit patient/care partner health outcome goals, communicate about deprescribing with patients and care partners, and align medications with goals of care, and an Epic template for communicating deprescribing recommendations to the PCP (attached). This document was developed in collaboration with 3 clinical pharmacists at JHCP and KPCO and closely adapted from the approach and language they use when calling patients with dementia and their care partners on the phone.

Intervention Fidelity:

1. Intervention adherence will be measured using a REDCap survey, which will enable us to monitor in real time and address issues immediately. The survey will be sent to pharmacists electronically together with the appointment information for each intervention telehealth visit. It will consist of a checklist that pharmacists will use to report which intervention elements occurred, any protocol deviations beyond their control (eg, dyads canceling a meeting), and the time required to complete each task in the intervention. We will calculate intervention fidelity as the proportion of dyads who participate in 2 of 2 pharmacist phone calls based on documented status reports.

2. We will calculate the proportion of eligible dyads that opt out of the intervention, and the proportion of pharmacist messages to the PCP that receive an acknowledgement or response (captured in the EHR).

3. To evaluate the content of the intervention being delivered, we will analyze a random sample of audiorecorded phone calls between pharmacists and dyads. We will use a fidelity checklist to determine the extent to which the pharmacists deliver the key elements of the intervention: 1) Assessing for medication-related problems (adherence issues, potential adverse effects, care partner strain); 2) Eliciting the dyad's key health outcome goals for the patient's health; and 3) Aligning medications with goals of care. We will also review the pharmacist-physician communication in the EHR to calculate the proportion of templates that are properly completed. This will enable us to provide feedback to the pharmacists in real time to address barriers to achieving high fidelity.

5.3 Concomitant Interventions

We do not have any concomitant interventions. All medical care will proceed in according to the decisions of the patient, care partner and primary care provider.

5.4 Adherence Assessment

There is no planned adherence assessment given the nature of the intervention.

6 STUDY PROCEDURES

6.1 Schedule of Evaluations

Assessment	Identify eligible population	Baseline: scheduling phone call (Day 0 + 28 days)	3 months post enrollment (Day 90 + 45 days)
Inclusion/Exclusion Criteria	X		
Patient demographics and diagnoses	X		
Care partner demographics		X	
Chronic medication count		X	X
Patient-level Medication Regimen Complexity Index (pMRCI)		X	X
Family Caregiver Medication Administration Hassles Scale (FCMAHS)		X	X

Feasibility measures			
Proportion of dyads that opt out	X		
Proportion of participants with data elements available to calculate pMRCI			·
		Throughout	intervention
Response rate and completion time for FCMAHS		Х	X
Proportion of pharmacist messages to PCP that receive			
acknowledgement or response		Throughout	intervention
Number of contacts between		Inoughout	
pharmacist and PCP and between pharmacist and dyad			
		Throughout	intervention
Time required by pharmacist to complete intervention			X
Type of recommendations made by pharmacist, acceptance rates for recommendations			X
Fidelity measures			
Proportion of intervention elements successfully completed by pharmacist			X

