5.1 Interventions, Administration, and Duration

1) The mailing sent to patients' homes will be no more than 3 pages and will consist of an informational brochure introducing the idea of discontinuing unnecessary or potentially inappropriate medications. This approach is based on an established model of patient-centered deprescribing and is adapted from a direct-to-consumer deprescribing intervention for older adults on benzodiazepines.^{34,35} Materials are designed to engage care partners and invite them to discuss medication-related concerns with the pharmacist. The informational brochure will include mention of how to plan for a telehealth visit with a clinical pharmacist to discuss medication optimization and reasons why some people may benefit from taking fewer medicines. It will encourage care partners to discuss their key health outcome goals for the patient, and medication-related activities that the dyad finds helpful and feasible vs. unhelpful or difficult. The brochure will include instructions NOT to discontinue any medications without talking to the clinical pharmacist or the patient's primary care clinician.

2) As described in Section 4.3, dyads who do not opt out (and dyads who opt in) will be called by the project assistant to assess interest and schedule the pharmacist consult approximately 14 days after mailing the intervention materials.

Intervention group:

3) The project assistant will schedule the telehealth visit with the clinical pharmacist to occur within the next 4 weeks.

4) After scheduling the pharmacist consult, the project assistant will offer care partner the option of completing the secondary outcome measure, the Family Caregiver Medication Administration Hassles Scale (FCMAHS). They will obtain verbal consent for the FCMAHS when administering it over the phone (see script). If the care partner does not wish to complete the FCMAHS over the phone during the scheduling phone call, the project assistant will offer to call back before the pharmacist visit (up to 28 days) or to later e-mail the care partner a link to an electronic version. The FCMAHS will be administered again 3 months after the enrollment phone call.

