6.2.2 Enrollment, Baseline, and/or Randomization

Enrollment

Project assistants will mail study materials with opt-out provisions to the homes of 60 patients (30 at each site). Dyads who do not opt out (or who opt in) will be called by the project assistant approximately 14 days later to describe the pharmacist consult and assess interest. Enrollment will be defined as the date of this phone call.

Baseline Assessments

The baseline point will be defined as the date of the enrollment phone call, whether or not dyads are randomized to the intervention or delayed intervention control group.

Randomization

Dyads who do not opt out (or who opt in) will be randomized to the immediate or delayed intervention group prior to the enrollment/scheduling phone call using computergenerated random numbers. The intervention group will be scheduled to have the pharmacist telehealth visit immediately (within 4 weeks) after enrollment. The delayed intervention group will receive the pharmacist-led component 3-4 months after enrollment. For dyads randomized to the delayed group, the project assistant will say, "I will call you back in about 3 months to remind you of the call with the pharmacist."

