10.2 Data Management

Unless otherwise mentioned, all data will be extracted from the Johns Hopkins EHR and the KPCO Virtual Data Warehouse, a quality controlled, research common data model that includes data from multiple KPCO data sources and includes the following domains: Pharmacy data, demographics, problem list diagnoses, and social history. Two identical instances of the REDCap database will be used for data collection – one at each site. Data from VDW will be pulled directly into REDCap; data from EHR will be manually entered into REDCap, downloaded and cleaned; data from pharmacist fidelity measures will be manually entered.

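### An e-mailed baseline FCMAHS may be completed after the pharmacist visit in the immediate arm only, because the limit that protects the phone version is not applied to the e-mailed link

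*Combined protocol and SAP*

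**What the plan says.** - **Baseline window.** Section 6.1 puts chronic medication count, pMRCI and FCMAHS in one column, "Baseline: scheduling phone call (Day 0", with plus or minus 28 days.
- **Immediate-arm visit.** Section 5.1: "The project assistant will schedule the telehealth visit with the clinical pharmacist to occur within the next 4 weeks". Section 6.2.2 agrees: "pharmacist telehealth visit immediately (within 4 weeks) after enrollment".
- **Delayed-arm visit.** About 3 months in sections 4.3 and 5.1, and 3 to 4 months in sections 6.2.2 and 9.2.1.
- **Fallback for the baseline FCMAHS.** A care partner who does not complete the scale in the scheduling call is offered one of two routes. The assistant will "call back before the pharmacist visit (up to 28 days) or to later e-mail the care partner a link" to an electronic version. Sections 4.3 and 6.2.1 give the same rule. Section 11.2 takes verbal consent for either version but states a pre-visit limit only for the call-back.
- **Baseline anchor.** Section 6.2.2: "The baseline point will be defined as the date of the enrollment phone call", in both arms.
- **Analysis.** Sections 9.1 and 9.5 regress FCMAHS change scores on assignment. The multiple-imputation sentence stands in the pMRCI paragraph; the FCMAHS paragraph does not mention missing data.

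**The concern.** The pre-visit limit on the phone call-back shows that the plan wants this baseline taken before the intervention. The e-mail route does not carry that limit. A link sent after the scheduling call can be opened after the pharmacist visit and still fall inside the 6.1 window. Nothing in the plan excludes or flags such a response.

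A baseline taken after the visit may already contain part of the effect that the change score is meant to capture. This can happen in one arm only, so randomization does not balance it. The pilot tests no hypotheses, but sections 9.1 and 9.5 say that its estimates are to help plan the larger trial. An attenuated FCMAHS contrast, with a spread that mixes two kinds of baseline, would be carried into that planning.

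**Working it through.** The plan gives no figure for e-mail use or for the timing of e-mailed responses, so there is none to reproduce. The precision statement in section 9.2 does not enter this point, except for its sample size and attrition rate.

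**1. Overlap of the windows (days after the scheduling call)**

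| | Pharmacist visit | Baseline window after the call | Overlap |
|---|---|---|---|
| Immediate arm | 0 to 28 | 0 to 28 | 28 days |
| Delayed arm | about 90 to 120 (30 days per month) | 0 to 28 | 0 days |

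**2. Which FCMAHS baselines are exposed**

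- Completed during the scheduling call: before the visit, not exposed.
- Phone call-back: must precede the visit, not exposed.
- E-mailed link: limited only by Day +28. For a visit on Day 14, for example, the link could be answered on any of the next 28 − 14 = 14 days and still count as in window.

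**3. Share affected (assumptions, not in the documents)**

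Let e be the share of immediate-arm FCMAHS completers who use e-mail, and p the share of those who answer after the visit. The affected share is q = e × p.

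- e = 0.10, p = 0.5: q = 0.05
- e = 0.40, p = 0.5: q = 0.20

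Section 9.2 gives 30 dyads per arm with 10% attrition, so 30 × 0.9 = 27. If all 27 completed the scale, q = 0.05 to 0.20 would be 1.35 to 5.4 forms, or about 1 to 5. The FCMAHS is optional, so the number of completers may be lower.

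**4. Effect on the contrast**

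Let D be the true arm difference in change and f the fraction of the effect already present when a post-visit baseline is taken. The expected contrast is

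(1 − q) × D + q × (1 − f) × D = (1 − q × f) × D.

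| q | f = 0.25 | f = 1 |
|---|---|---|
| 0.05 | 1 − 0.0125 = 98.75% of D | 1 − 0.05 = 95% of D |
| 0.20 | 1 − 0.05 = 95% of D | 1 − 0.20 = 80% of D |

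The value f = 1 is the worst case. Under section 5.1 the pharmacist first messages the PCP and calls the dyad to implement changes only after approval, so a response given soon after the visit may precede any change in the regimen.

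**The case against.** The strongest reply is that the exposure is narrow. The FCMAHS is first offered in the scheduling call, the call-back is already protected, and e-mail is a fallback for a secondary measure in a pilot without hypotheses. After the visit is also not the same as after a medication change. All of this stands. It limits the size of the problem but does not close the gap.

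Three stronger readings are tempting, and the documents do not support them.

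- **That the e-mailed form has no time limit at all.** The Day +28 bound in section 6.1 covers it. What is missing is a limit tied to the visit.
- **That baseline pMRCI and medication count can equally be post-visit.** A reader might infer this from the 6.1 window together with section 10.2, where "data from EHR will be manually entered into REDCap, downloaded and cleaned". But section 6.2.2 fixes baseline at the call date, and section 6.2.3 repeats that definition. Section 6.2 ties the eligibility medication list to the date of enrollment. Section 10.2 also says that data from the Virtual Data Warehouse (the KPCO source) are pulled directly, and manual entry says how data are transferred, not the date they describe. What remains is a tension in wording: 6.1 allows 28 days either side, and the medication-count definition uses an assessment date that it does not define.
- **That a large share of all baselines would follow the visit because the two windows coincide.** That would require baselines spread evenly over the window, which does not fit a scale offered during the Day 0 call or EHR values anchored to that call.

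A fair point about the remedy is that setting late responses to missing creates missing baselines in one arm only. The fix allows for this.

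**Conclusion.** The concern holds for the e-mailed baseline FCMAHS. The plan permits completion after the pharmacist visit in the immediate arm and, given the delayed arm's visit date, not in the other. Under the stated assumptions 5% to 20% of immediate-arm baselines are affected, and 80% to 98.75% of the FCMAHS contrast is retained. The documents supply none of e, p or f. The direction toward zero assumes that any early effect has the same sign as the effect at 3 months. The upper bound on attenuation assumes that the early effect is no larger than the later one.

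For pMRCI and chronic medication count the finding is only that sections 6.1 and 6.2.2 should be reconciled. This is an inexpensive improvement that should be made; it does not undermine the pilot.

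**What to change.** 1. In sections 4.3, 5.1, 6.1, 6.2.1 and 11.2, apply the existing call-back limit (before the pharmacist visit, and no more than 28 days after the call) to phone and e-mail alike.
2. Set the baseline link to expire at the appointment time.
3. Record the FCMAHS completion date and the visit date for every dyad.
4. In section 9.5, state that a post-visit response is not used as baseline in the main change-score analysis. Treat it as missing under the planned multiple imputation, extended explicitly to the FCMAHS, and add a sensitivity analysis that includes these responses.
5. In section 6.1, state that for pMRCI and medication count the 28 days either side is a collection window and that values describe status on the enrollment call date, as section 6.2.2 implies.

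The cost is protocol wording, a link expiry and two date fields. The downside is a few more missing baseline forms in the immediate arm only: under the assumptions above, at most about 1 to 5 of 27, and fewer if the deadline prompts earlier responses. Visit timing and care do not change.

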6.2 Description of Evaluations

Pilot study evaluations will consist of: 1) assessing baseline eligibility criteria; 2) assessing the intervention for feasibility and acceptability; 3) assessing outcomes of the future pragmatic trial for measurement feasibility; and 4) assessing intervention fidelity.

Definitions of the data elements and sources are itemized below. Unless otherwise mentioned, all data at JHCP will be extracted from the EHR. All data at KPCO will be extracted from the KPCO Virtual Data Warehouse, a quality controlled, common data model that includes data from multiple KPCO data sources covering enrollment, utilization, pharmacy, demographics, mortality, problem list diagnoses, and social history, among other domains.³⁶

Inclusion/ exclusion criteria: As previously described (section 4.1). Data elements will include age, diagnosis codes, current medications on the date of enrollment (see definition "chronic medication count" below). Chronic diagnoses will be from a list of 86 chronic conditions itemized in the Multiple Chronic Conditions Chartbook.³⁷ We have developed a method of counting chronic medications that uses a consensus-based list of Generic Product Index (GPI) categories to be included for polypharmacy estimates.

Patient demographics and diagnoses: Age, gender, and race/ethnicity will be collected from the EHR. ICD-10 codes will be used to identify diagnoses from visit billing codes, hospital and emergency department claims diagnoses, and problem list diagnoses.

Care partner demographics: Age, gender, race/ethnicity, relationship to patient, and health literacy ("How confident are you filling out medical forms by yourself?") will be asked by the project assistant during the scheduling phone call.

Chronic medication count: We will use the approach refined in Optimize to define chronic medication use as any prescription medication for which the patient had at least a 28-day supply on the assessment date.³² We selected a 28-day supply (rather than a supply for a longer time period) because some medications (such as opioid medications) are mostly dispensed in 28-day supplies. Chronic medications exclude the following domains identified by 2-digit GPI codes: vaccines, toxoids, allergenic extracts, oxytocics, local anesthetics—parenteral, general anesthetics, antiseptics and disinfectants, antidotes, diagnostic products, chemicals, and medical

devices. We are examining different methods of identifying chronic medications in the Johns Hopkins EHR.

Patient-level Medication Regimen Complexity Index (pMRCI): Scores are derived from weighted values of regimen components (eg, dosage formulations, frequencies, and specific instructions).² We will adapt an algorithm developed and tested by [name] team to extract pre-specified variables from the EHR and calculate pMRCI scores in REDCap.²⁰ The data analytics teams at both institutions will determine the steps necessary to further adapt the pMRCI for use within the existing EHR systems. In doing so, we will build on methods developed by JHU researcher, [name], who automated the pMRCI within an EHR and calculated pMRCI scores for 70,000 patients.^{3,38} Similar EHR adaptations of the pMRCI by other researchers will also serve as a foundation for our work.¹⁰⁹

Family Caregiver Medication Administration Hassles Scale (FCMAHS): Collected from family care partners at baseline by the project assistant and again at approximately 3 months after enrollment. For care partners who are unable to complete the FCMAHS by phone, we will examine the feasibility of administering it electronically by e-mailing them a link. See attached patient intervention materials. Project assistants will record administration time when the FCMAHS is administered over the phone. Care partners will be asked to record administration time when it is self-administered electronically.

Feasibility measures:

Proportion of dyads that opt out: Will be assessed from the patient recruitment/ tracking log completed by project assistants.

Proportion of participants with data elements available to calculate pMRCI: Will be calculated based on the algorithm developed above.

Response rate and completion time for FCMAHS: Completion time will be collected by project assistants when they administer the FCMAHS on the telephone, and via self-report when it is administered electronically. The response rate using both modes of administration will be assessed.

Proportion of pharmacist messages to PCP that receive an acknowledgement or response; number of contacts between pharmacist and dyad; number of contacts between pharmacist and PCP: Project assistants will extract these data from the EHR at 3 months.

Time required by pharmacist to complete the intervention: Pharmacists will be asked to complete a REDCap survey. The link will be sent to them via e-mail to complete after each patient-care partner telehealth visit.

Fidelity measures:

Proportion of intervention elements successfully completed by pharmacist: A sample of audiorecorded telehealth visits between pharmacists and dyads will be scored by project assistants using a fidelity checklist.

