 This is the standard approach that clinic staff use to call patients with dementia on the phone and identify their care partners during the course of clinical care. As the intervention is designed to address the needs of care partners and requires their participation, the project assistant will ask to speak with the care partner first. Because some patients with mild or moderate dementia may be interested in hearing about the program, the project assistant will offer to describe it to the patient as well.
- Patients who are unwilling or unable to identify a care partner who helps them manage their medicines will be excluded. The project assistant will document the reasons for ineligibility in a REDCap Screening Log.
- The project assistant will briefly describe the pharmacist consult to the care partner. If the care partner agrees, the project assistant will schedule the pharmacist call, which will occur immediately (within 4 weeks) for the intervention group and at approximately 3 months for the delayed intervention control group.

4) If patients or care partners opt out during the phone call, the project assistant will document the reason (eg, no time to participate, not interested) in a REDCap Screening Log.

5) Dyads randomized to the delayed intervention group will be told that they will receive another phone call from the project assistant in approximately 3 months to remind them of their appointment with the clinical pharmacist.

6) After scheduling the pharmacist consult, project assistants will offer care partners in both groups the option of completing the secondary outcome measure, the Family Caregiver Medication Administration Hassles Scale (FCMAHS). For care partners who are interested in completing the FCMAHS, project assistants will obtain verbal consent when administering the measure over the phone (see script). If the care partner does not wish to complete the FCMAHS over the phone during the scheduling phone call, the project assistant will offer to call back before the pharmacist visit (up to 28 days) or to later e-mail the care partner a link to an electronic version.

5 STUDY INTERVENTIONS

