5) Using comprehensive medication management (CMM) as a foundation, the pharmacist will call the patient-care partner dyad to assess for medication-related problems, such as issues with adherence, potential adverse effects and caregiver strain related to medication management. Clinical pharmacists are already embedded in both pilot clinics and throughout their parent healthcare systems, and are conducting CMM phone calls with patients. The clinical pharmacists in ALIGN have considerable experience doing medication reviews with older adults, patients with dementia and care partners. They will use a script that was closely adapted from templates that are currently being used by embedded clinical pharmacists in both healthcare systems. The pharmacists will use these guiding questions to elicit the dyad's goals and priorities for the patient's health in

order to align medications with goals of care (see attached template). We anticipate that the intervention phone call will take up to 1 hour.

6) The pharmacist will then develop an evidence-based deprescribing communication, which will be routed to the PCP via the EHR using a standardized template (see attached). The pharmacist will contact the PCP as per usual clinical practice. The template will encourage the PCP to respond to the pharmacist either to accept the recommendations, to ask questions or to raise concerns.

7) With the PCP's approval, the pharmacist will call the dyad to implement the recommendations and document the changes in the EHR. An updated medication list will be mailed to the dyad. All decisions about discontinuation or continuation of medications will be made by the PCP and patient/ care partner.

Delayed intervention group:

Steps 1-2 will be identical to the intervention group. For participants randomized to the delayed intervention control group, the project assistant will schedule the pharmacist consult in approximately 3 months.

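### The supply-based chronic medication count has no rule for discontinued drugs, so a drug stopped before the 3-month assessment can still be counted

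*Combined protocol and SAP*

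**What the plan says.** All references are to the combined protocol and SAP.

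- **Count.** Section 6.2 defines chronic use as "any prescription medication for which the patient had at least a 28-day supply on the assessment date". The 28-day threshold was chosen because "some medications (such as opioid medications) are mostly dispensed in 28-day supplies". Certain product classes are excluded, but nothing is said about a drug whose order was discontinued before the assessment.
- **Site difference.** Of the other site, Section 6.2 says "We are examining different methods of identifying chronic medications in the Johns Hopkins EHR".
- **Timing of stops.** Section 4.3 schedules the pharmacist call "immediately (within 4 weeks) for the intervention group". Section 5.1, step 7, adds: "With the PCP's approval, the pharmacist will call the dyad to implement the recommendations and document the changes in the EHR". No day is given for this step.
- **Assessment.** Section 6.1 repeats the count and pMRCI at day 90, with 45 days allowed either side.
- **pMRCI.** Under Section 6.2 an adapted algorithm is to "extract pre-specified variables from the EHR and calculate pMRCI scores in REDCap". The medication list it reads is not stated.
- **Use.** Sections 3 and 9.4 compare the two measures as candidates for the primary outcome of the later pragmatic trial. Change in each is one of the things measured.

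**The concern.** A supply rule is reasonable for deciding who is eligible or how many drugs a patient takes. At follow-up in a deprescribing study it can miss the event that the intervention is meant to produce. A patient may have stopped a drug with the physician's agreement and still have a fill whose days' supply runs past the assessment date. Followed as written, the rule counts that drug.

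During the first 3 months the control arm receives only the mailing, so it is reasonable to expect fewer stops there. Carry-over would then take more from the intervention arm's change and shrink the between-arm difference in the count. The pilot's estimates of change are meant to help plan the larger trial and to inform the choice between count and pMRCI. A count that is slow to register stops could look less responsive than it is.

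**Working it through.** The plan gives no figure on this point, so there is none to reproduce. The check asks how often a drug stopped on day s still counts on assessment day A.

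**Inputs from the documents**
- The pharmacist visit falls by day 28 (Section 4.3). The stop comes later, after physician approval and a second call (Section 5.1).
- A is nominally 90 and may lie from 90 − 45 = 45 to 90 + 45 = 135 (Section 6.1).

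**Assumptions (not in the documents)**
- Fill length L is 30 or 90 days.
- The stop day s is 14, 28, 42 or 56.
- The last fill before the stop is uniformly timed, and there is no refill after the stop.

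**Two readings of the 28-day rule**
1. *Covering fill:* a fill of at least 28 days whose supply reaches day A. This fits the dispensing rationale better. Share still counted = max(0, (L − (A − s))/L).
2. *In hand:* at least 28 days of supply remain on day A. Share still counted = max(0, (L − 28 − (A − s))/L).

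**Day 90**

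| Stop day | Covering fill, L = 90 | In hand, L = 90 | Covering fill, L = 30 |
|---|---|---|---|
| 14 | 14/90 = 16% | 0% | 0% |
| 28 | 28/90 = 31% | 0/90 = 0% | 0% |
| 42 | 42/90 = 47% | 14/90 = 16% | 0% |
| 56 | 56/90 = 62% | 28/90 = 31% | 0% |

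On the covering-fill reading, carry-over at day 90 needs a fill longer than 90 − s days: 76, 62, 48 and 34 days for the four stop days.

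**Mixed fills, day 90, covering fill.** If 25%, 50% or 75% of drugs are on 90-day fills and the rest on 30-day fills, the share still counted is 0.311 × (0.25, 0.50, 0.75) = 8%, 16%, 23% for a day-28 stop. For a day-42 stop it is 0.467 × the same shares = 12%, 23%, 35%.

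**Edges of the window, covering fill, day-28 stop**
- Day 45: (90 − 17)/90 = 81% with 90-day fills and (30 − 17)/30 = 43% with 30-day fills.
- Day 135: A − s = 107 exceeds both fill lengths, so 0%.

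The permitted window therefore allows carry-over at its early edge even with short fills.

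**The in-hand reading is not harmless.** It carries over fewer stopped drugs, but it also misses drugs still in use. A continued drug counts with probability (L − 28)/L, which is 62/90 = 69% for 90-day fills and 2/30 = 7% for 30-day fills. For a day-42 stop with 90-day fills, the expected difference per stopped drug is 0.689 − 0.156 = 0.533. The covering-fill reading gives 1 − 0.467 = 0.533, the same shortfall.

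**The case against.** A reader might infer that the lag makes Aim 2a favour pMRCI: stops are documented in the EHR, pMRCI is built from EHR variables, and so pMRCI sees the stop at once while the count does not. The documents do not support this.

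- Section 6.2 never says that pMRCI uses active orders. It names one default source per site for all data: the EHR on the Johns Hopkins side and, at KPCO, the Virtual Data Warehouse, which includes pharmacy data. Sections 3 and 9.4 say the count also comes from the EHR. If both measures use one medication list, they share the lag.
- No rule selects the measure with the larger effect. Aim 2a is mainly descriptive, the stated correlation is at baseline and so untouched by carry-over, and the regression on assignment is specified for pMRCI and not for the count.

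Other objections also have force. The Johns Hopkins method, covering half of the 60 planned dyads, is not settled. The count relies on algorithms from an earlier trial (OPTIMIZE), and whether they handle discontinued drugs cannot be seen here. The size depends wholly on assumed fill lengths and stop days, and it is zero at day 90 with 30-day fills. Accepted recommendations are extracted from the EHR separately, which gives a partial check on stops.

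The remedy can also introduce bias. Intervention-arm stops are documented by the pharmacist as a study step, and no matching process covers control-arm stops in the first 3 months. Removing drugs by recorded stop date could therefore favour the intervention arm.

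These points limit the size, the reach and the form of the remedy. They leave standing the fact that the written definition goes by supply and does nothing with a discontinued drug.

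**Conclusion.** The point holds as a gap in a stated rule. As defined, the count can include a drug already stopped, and the effect on it is biased toward zero if the intervention arm stops more drugs. This is firm at most for KPCO.

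The size is not established. On the assumptions above it ranges at day 90 from nothing (30-day fills) to 62% of stopped drugs (90-day fills, covering-fill reading, day-56 stop). It is larger for early assessments and, for a day-28 stop, absent at day 135. Whether the comparison with pMRCI is distorted cannot be determined until pMRCI's medication list is stated. In a pilot without statistical hypotheses this is a modest improvement to make before extraction, not a threat to the study.

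**What to change.** 1. State whether the 28-day rule means a fill covering the assessment date or 28 days still in hand, and use the same meaning at both sites.
2. At 3 months, report the count two ways in both arms and at both sites: the supply-based count as defined, and a count that also removes any drug with a recorded discontinuation date on or before the assessment date.
3. State the medication list from which pMRCI is computed and handle discontinued drugs in it the same way, so that the Aim 2a comparison does not mix responsiveness with data-source lag.
4. State the limitation of each version: the supply-based count may understate stops, and the adjusted count may favour the intervention arm because its stops are recorded more fully. Neither should be read alone.

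The cost is a discontinuation-date field in the extraction and one more reported count. The changes made by the pharmacist are already documented in the EHR. Availability at KPCO must be confirmed, since the warehouse domains listed in Sections 6.2 and 10.2 do not mention discontinuation dates. The Johns Hopkins method is still being chosen, so this is cheap to settle now.
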